17. ELECTRONIC PATIENT REPORTED OUTCOMES DIARY COMPLIANCE

Electronic patient reported outcomes diary compliance at each 1-month period (including baseline, Month 1, 2, 3) as well as for treatment period overall (Month 1 through Month 3) will be calculated.

Treatment comparisons for diary compliance for each period will be performed separately using an ANOVA with treatment in the model.

Electronic patient reported outcomes diary compliance will be presented for the SAF.

17.1. DERIVATIONS

Diary compliance at each period is calculated as:

$$\frac{\text{Actual number of diary days in the period} * 100}{\text{Expected number of diary days in the period}}$$

Expected number of Diary days is calculated as date of injection at the end of interval minus date of injection at the beginning of the interval +1.

18. EFFICACY OUTCOMES

18.1. EFFICACY MEASURES

18.1.1. MIGRAINE AND HEADACHE MEASURES

Headache information will be collected via an ePRO diary. Patients will need to enter ePRO diary data daily beginning from V2 and continuing until V6. Should there be duplicate headache dates, the date with the later study date/time should be used. A summary table and a listing of the responses to each diary question will be presented.

Information recorded in the ePRO diary, the possible responses, and the assignment to the type of headache is presented in Table G:

Document: CCI

Author: PPD

Version Number:

3.0

Version Date:

19May2023

CCI

Table G: ePRO Diary Questions, Responses, and Assignment to Headache Type

QUESTION	RESPONSE	HEADACHE ASSIGNMENT
Q1. Yesterday, did you have a headache that lasted for thirty minutes or more?	Yes	
	No ^a	
Q2. Enter the total number of hours you had a headache yesterday.	Range 1 to 24	If ≥ 1 the headache will be counted as a headache day.
Q3. Yesterday, what was the worst headache pain?	Mild	
	Moderate	Migraine Criteria A
	Severe	Migraine Criteria A
Q4. Yesterday, was the headache throbbing or pounding?	Yes	Migraine Criteria A
	No	
Q5. Yesterday, was the headache just on the right or left side of your head?	Yes	Migraine Criteria A
	No	
Q6. Yesterday, was the headache made worse by your usual daily activity?	Yes	Migraine Criteria A
	No	
Q7. Yesterday, did the headache come with sensitivity to light and sound?	Yes	Migraine Criteria B
	No	
Q8. Yesterday, did you feel sick to the stomach or throw-up with the headache?	Yes	Migraine Criteria B
	No	
Q9. Yesterday, did you have your menstrual period (if female)?	Yes	
	No	
Q10. Yesterday, did you experience aura?	Yes	
	No	
Q11. Yesterday, did you experience any warning symptoms (prodrome symptoms) that a migraine was coming other than aura?	Yes	
	No	
Q12. Yesterday, did you take any medicine for your headache?	Yes	Medication will only count as headache medication on a day a headache occurred.
	No	

^a If "No" is answered for Q1, then the patients will skip Q2 - Q6, only answer questions Q7 - Q12 by removing reference to headache.

Migraine and Headache Endpoint Definitions are provided in Table H:

Table H: Migraine and Headache Endpoint Definitions

Diagnosis	Definition/Criteria
-----------	---------------------

Document: **CCI**

Author: **PPD**

Version Number:

3.0

Version Date:

19May2023

CCI

Migraine headache	
A headache, with or without aura, of ≥ 30 minutes duration, with both of the following required features (A and B):
 
A. At least 2 of the following headache characteristics:
 
 • Unilateral location • Pulsating quality • Moderate or severe pain intensity • Aggravation by or causing avoidance of routine physical activity 
AND
 
B. During headache at least 1 of the following:
 
 • Nausea and/or vomiting • Photophobia and phonophobia 
(Definition adapted from the standard IHS ICHD-3 definition)

Probable migraine headache	A headache of ≥ 30 minutes duration, with or without aura, but missing one of the migraine features in the IHS ICHD-3 definition. To be exact, it meets either at least two A criteria and zero B criteria, or one A criteria and at least one B criteria.
Migraine headache day (primary objective)	A calendar day on which a migraine headache or probable migraine headache occurs.
Migraine headache attack	Beginning on any day a migraine headache or probable migraine headache is recorded and ends when a migraine-free day occurs.
Non-migraine headache	All headaches of ≥ 30 minutes duration not fulfilling the definition of migraine or probable migraine.
Non-migraine headache day	A calendar day on which a non-migraine headache occurs.
Headache day	A calendar day on which any type of headache occurs (including migraine, probable migraine, and non-migraine headache).

Primary Measure: $\geq 50\%$ Percent Reduction in migraine headache days

The primary measure is the percent reduction from baseline in migraine headache days (per 30-day period). A migraine headache day is defined as a calendar day on which a **migraine or probable migraine** occurs.

The percent change from baseline in the number of migraine headache days will be calculated for any post-baseline 30-day period as:

Document: CCI

Author: PPD

Version Number:

3.0

Version Date:

19May2023

CCI

$$-1 * \frac{100 \times (\# \text{ of MHD in Month Y} - \# \text{ of MHD in baseline period})}{\# \text{ of MHD in baseline period}}$$

A 50% responder (Participant with $\geq 50\%$ reduction from baseline in migraine headache days): is defined as Yes, if any participant who has a $\geq 50\%$ reduction in the total number of migraine headache days in a 30-day period relative to baseline period, as No if otherwise. Therefore, if the percent change from baseline in the number of migraine headache days is $\geq 50\%$, the participant will be counted as an 50% responder.

Change from baseline in the number of monthly migraine headache days in each 30-day period will be summarized from daily data for each patient in that period (including approximately 30 days of daily data from the baseline period prior to randomization, 3 months of daily data during double-blind treatment period).

The daily ePRO data will reflect whether the patients meet the migraine / probable migraine criteria; those data will be aggregated, and the number of migraine headache days will be provided for each of the 30-day periods.

18.1.2. ADJUSTING FOR THE NUMBER OF DAYS WITH NON-MISSING DIARY DATA IN THE PERIOD:

In calculating the number of migraine headache days for each period, if the period is not equal to 30 days, the number of migraine headache days will be adjusted by multiplying the number of migraine headache days by $(30/x)$ where “x” is the total number of non-missing diary days in the period.

This approach to missing ePRO diary data assumes that the rate of migraine headaches per day is the same with missing and non-missing ePRO diary days, and it is missing at random. The same approach will also be applied to secondary and exploratory measures that are derived from the ePRO data.

Additionally, if the ePRO compliance rate (please refer to Section 17) for a monthly interval is $\leq 50\%$, then all endpoints to be derived from the ePRO diary data for that one-month period will be considered missing. For a participant who discontinued early in the double-blind treatment

Document: **CCI**

Author: **PPD**

Version Number:

3.0

Version Date:

19May2023

CCI

phase, compliance rate for the last month of that study period will be calculated with the denominator of the maximum of 30 and the total number of calendar days in that month.

Secondary and Exploratory Migraine and Headache Measures

Number of migraine headache days with acute (abortive) medication use is calculated as the number of calendar days in a 30-day period on which migraine or probable migraine occurs and acute (abortive) medication is used (based on the response to question 12 in the daily diary questions, Table G).

Weekly migraine headache days is defined as is calculated as the number of migraine headache days in a 7-day period on which a migraine headache occurs. For each month, the first 7 calendar days will be counted as week 1, the second 7 calendar days will be counted as week 2, the third 7 calendar days will be counted as week 3, and the rest of days will be counted as week 4.

Number of migraine headache hours is calculated as the total number of headache hours in a 30-day period on days when a migraine or probable migraine occurs.

Number days with acute (abortive) medication use is calculated as the number of calendar days in a 30-day period on which an acute (abortive) medication is used (based on the response question 12 in the in the daily diary questions, Table G).

Number of headache days is calculated as the number of calendar days in a 30-day period on which a headache occurs (includes migraine, probable migraine, and non-migraine).

Number of moderate to severe headache days is calculated as the number of calendar days in a 30-day period on which a headache occurs with a moderate or severe severity (based on Q3 response, Table G.)

Number of migraine attacks per 30-day period is calculated as the number of sets of consecutive days with migraine or probable migraine separated by at least one migraine-free day. For example, a migraine or probable migraine starting on 5JAN and ending on 6JAN will result in a migraine/probable migraine-free day on 7JAN (assuming that there is no migraine/probable migraine on 7JAN). This will count as 1 migraine attack that started on 5JAN and ended on

Document: **CCI**

Author: **PPD**

Version Number:

3.0

Version Date:

19May2023

CCI

6JAN. For a migraine attack that begins in one 30-day period but ends in another, only 1 migraine attack will be counted in the first of the 2 periods. For example, in the case of 7 days of consecutive migraine/probable migraine headache with 3 days in the baseline period and 4 days in Month 1, only 1 migraine attack will be counted in the baseline period; the 4 days of migraine/probable headache in Month 1 will not be counted as a migraine attack in Month 1.

Mean severity of migraine or probable migraine headaches on migraine headache days will be calculated at each period (including baseline and any post-baseline periods). For the calculation of mean severity, for days with migraine or probable migraine, severity varies from 1 to 3 with 1=mild, 2=moderate, and 3=severe. The mean severity for each period will be calculated as:

$$\frac{\text{Sum of Severity of migraine headache days in the period}}{\text{\# of migraine headache days in the period}}$$

For periods with zero migraine headache days, the mean severity is considered not applicable hence missing in the analysis data set.

An X% responder is defined as Yes, if any patient who has a $\geq X\%$ reduction in the total number of migraine headache days in a 30-day period relative to baseline period, as No if otherwise. Therefore, if the percent change from baseline in the number of migraine headache days is $\geq X\%$, the patient will be counted as an X% responder. In other words, if the response rate defined above in a month is $\geq X\%$, then the patient will be an X% responder in that month. In addition to the primary response endpoint with X=50, indicators of X% responders will be derived for X= 75, and 100. The same calculation that was used for percent change from baseline in the number of migraine headache days for the primary endpoint will be used for these endpoints as well.

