### 1.3. Schedule of Activities (SoA)

SP I – Screening		SP II – Prospective Baseline	SP III – Double-Blind Treatment				ET	Comments
Visit 1 procedures may be conducted over more than 1 day as long as all activities are completed within the allowable visit tolerance.								
Visit Number	1	2	3	4 a	5 a	6		
Month relative to randomization (V3)	*	**		1	2	3		
*Screening lasts from 3 to 30 days.
 
** Eligibility is determined between a minimum of 30 days and a maximum of 40 days. Investigators have up to 5 additional days, if needed, to schedule participant's Visit 3 appointment.
 
For scheduling purposes, a month is 30 days.

Interval allowance (days)			-	±2	±2	±2		
Telephone Visit				X	X			See footnote a.
Informed consent	X							The ICF must be signed before any protocol-specific tests or procedures are performed.
Inclusion and exclusion, review and confirm	X	X	X					
Demographics	X							
Medical history	X							
Substance use	X							Substances: alcohol, caffeine, nicotine, tobacco
Concomitant medications	X	X	X	X	X	X		
AE	X	X	X	X	X	X		Any events that occur after signing the ICF are considered AEs as defined in Section 10.3.
Physical Evaluation								
Height	X							
Weight	X							
12-lead ECG (local)	X					X	X	
ECGs should be collected prior to blood draws. Participants should be supine for approximately 5 to 10 minutes before ECG collections and remain supine but awake during the ECG collection.
 
See Section 8.2.3 for additional details.

Vital signs	X		X			X	X	Includes body temperature, sitting blood pressure, and pulse.

SP I – Screening		SP II – Prospective Baseline	SP III – Double-Blind Treatment				ET	Comments
Visit 1 procedures may be conducted over more than 1 day as long as all activities are completed within the allowable visit tolerance.			1	2	3	4 a	5 a	6
Visit Number	1	2						
Month relative to randomization (V3)	*	**		1	2	3		
*Screening lasts from 3 to 30 days.
 
** Eligibility is determined between a minimum of 30 days and a maximum of 40 days. Investigators have up to 5 additional days, if needed, to schedule participant's Visit 3 appointment.
 
For scheduling purposes, a month is 30 days.

Interval allowance (days)			-	±2	±2	±2		
Telephone Visit				X	X			See footnote a.
								Blood pressure and pulse will be measured in triplicate after participant has been sitting for at least 5 minutes, and prior to blood draws.
Physical examination	X							

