#### 4.1.2. Study Period II: Prospective Baseline (Visit 2)

At Visit 2:

- Participants are to be set-up and trained on their ePRO diary and instructed to begin logging in daily (beginning the day of Visit 2) to the ePRO diary to answer questions about the occurrence of
  - headaches,
  - headache duration,

- headache features,
- severity of headache, and
- whether any acute headache medication was taken.
- Participants will record the name, dose, and date of any acute headache medication on a separate paper headache medication log.

NOTE: The headache medication log should be returned to site staff at the final office visit or early termination visit.

Processing of Visit 2 in IWRS triggers the initial shipment of study intervention; therefore, ensure Visit 2 is completed in IWRS promptly.

Sites will be notified via an eligibility report whether the participant met criteria and are eligible to be randomized at Visit 3 (See Section 4.1.3). Eligibility is assessed beginning on Day 30 through Day 40, if needed, of the prospective baseline period. Investigators have up to 5 additional days if needed to schedule participant's Visit 3 appointment.

**To avoid biased reporting, participants must not be told the number of migraine headache days on which study qualification is based.**

At either Visit 2 or Visit 3:

- If available and where local regulations and Ethical Review Boards allow, participants will also watch two training videos
  - Video 1: is designed to address participant expectation with regards to participation in trial which includes placebo and the difference between medical treatment and research
  - Video 2: self-injection of SC study intervention video

NOTE: If the participant watched the video at Visit 2, they do not need to watch the video again at Visit 3. However, if the participant watched 1 video at Visit 2, the participant must watch the remaining video at Visit 3.

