- A treatment-emergent low result is defined as a change from a value greater than or equal to the low limit at all predose/baseline visits to a value less than the low. Patients with all normal or high values at predose/baseline (no low values) will be included in the analysis of treatment-emergent low laboratory values.

Baseline monthly migraine headache days value for primary efficacy analysis is calculated with a time window of 30 to 40 days (normalized to 30 days).

Document: **CCI**

Author: **PPD**

Version Number:

3.0

Version Date:

19May2023

CCI

Participant population with baseline and post-baseline definitions by type of analysis can be found in Table F:

Table F: Participant Population with Baseline and Post-Baseline Definitions by Type of Analysis

Analysis	Participant Population	Baseline Observation	Post-baseline Observation(s)
Primary/secondary/exploratory efficacy analyses (repeated measures or average of observed monthly values)	ITT Set with a baseline and at least one post-baseline observation	Visit 3	All scheduled visits 3<Visits ≤ 6
Primary/secondary/exploratory efficacy analyses	ITT Set with a baseline and at least one post-baseline observation	Visit 3	Last of Visit 3.01-6
Quality of Life analyses	ITT Set with a baseline and at least one post-baseline observation	Visit 3	All scheduled visits 3<Visits ≤ 6
TEAEs	Safety Analysis Set	All Visits 1-3	All Visits 3.01-6
Serious adverse events, discontinuations due to adverse events	Safety Analysis Set	NA	All Visits 3.01-6
Treatment emergent abnormal laboratory values	Safety Analysis Set with normal laboratory values at all non-missing baseline visits (with respect to direction being analyzed) and who have at least one post-baseline observation	Low: Minimum value from Visits 1-3 High: Maximum value from Visits 1-3	Low: Minimum value from Visits 3.01-6 High: Maximum value from Visits 3.01-6

Document: **CCI**

Author: **PPD**

Version Number:

3.0

Version Date:

19May2023

CCI

Analysis	Participant Population	Baseline Observation	Post-baseline Observation(s)
Treatment emergent changes in temperature	Safety Analysis Set with normal temperature values at all non-missing baseline visits (with respect to direction being analyzed) and who have at least one post-baseline observation	Low: Minimum value from Visits 1-3 High: Maximum value from Visits 1-3	Low: Minimum value from Visits 3.01-6 High: Maximum value from Visits 3.01-6

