		Current or prior exposure to a CGRP antagonist	Non-Programmable-Study Team identified	1) Stats will create the list of patients who meet this IPD criteria. 2) Among those, the true IPDs will be manually added into non-programmable Excel spreadsheet.
		BMI ≥ 40 at baseline	Programmable - Stats	
		Positive or No urine drug screen prior to randomization	Programmable - Stats	For randomized patients if prior to Visit 3, a patient has a positive UDS result and a repeated UDS not done or last repeat UDS is positive or UDS never collected.
		Other inadvertent enrollment which is deemed clinically important by Lilly Medical	Non-Programmable-Study Team identified	Not all inadvertent enrollments will necessarily be considered clinically important.

Document: CCI

Author: PPD

Version Number: 3.0

Version Date: 19May2023

Category	Subcategory	Study-specific	Source	Comments
Data Quality	Missing Data	Diary compliance <=50% for half or more of patient's double-blind treatment phase participation	Programmable – Stats	
With <=50% ePRO compliance rate for half or more months of double-blind treatment phase, where "month" refers to a dosing interval. For example,
 
 • if patient remained in the study for 3 months (i.e., dose intervals), and >=2 months have epro compliance <=50%. • if patient remained in the study for 1 or 2 months (i.e., dose intervals), and >=1 months have epro compliance <=50%. 
Lost to follow-up patients' last month interval should not be included in the consideration above.
 
If a patient discontinued before Visit 4 or if total time in double-blind period was less than 2 weeks, the patient should not be counted here.

		Missing safety measurement: vital signs (Blood pressure, body temperature, pulse) at baseline or in SP III		
For randomized patients, if blood pressure, body temperature, or pulse are missing all baseline measures or missing all post-baseline measures during the double-blind treatment period.
 
For patients who discontinued due to "lost to follow up", if all postbaseline measures are missing, it is not an important protocol deviation

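### The diary adjustment in SAP 18.1.2 is triggered by period length, so a 30-day period with missing entries is left unadjusted

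*SAP*

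**What the plan says.** SAP 18.1.2 is headed as an adjustment for the number of days with non-missing diary data. Its operative sentence applies the factor 30/x "if the period is not equal to 30 days, the number of migraine headache days will be adjusted by multiplying", and defines x as the count of non-missing diary days in the period. The next paragraph says the approach "assumes that the rate of migraine headaches per day is the same with missing and non-missing ePRO diary days", and extends it to the secondary and exploratory diary measures. A month is set to missing only when diary compliance is 50% or less. Inclusion criterion 5 (Protocol 5.1) requires at least 80% of diary entries at baseline.

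The documents do not settle how long a period is:

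- SAP 18.1.1 says the percent change "will be calculated for any post-baseline 30-day period as" shown there.
- SAP Appendix 3, for the diary-compliance deviation, says a month "refers to a dosing interval". The Schedule of Activities allows Visits 4 to 6 to move by 2 days either way.
- SAP 17.1 counts expected diary days as the closing injection date minus "date of injection at the beginning of the interval +1".
- For baseline, Protocol 4.1.2 states: "Eligibility is assessed beginning on Day 30 through Day 40, if needed, of the prospective baseline period". SAP 6.2 describes the baseline count as taken over 30 to 40 days and normalised to 30.

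**The concern.** The trigger and the divisor measure different things: one is calendar length, the other is completeness. When a period is exactly 30 days long the condition is false, so no rescaling takes place however many entries are missing. A 29-day or 31-day period with the same gaps is rescaled.

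The monthly count feeds the primary 50% response, the 75% response and every diary-based change score. If the sentence is programmed as written, absolute results in both arms depend on which periods happen to last exactly 30 days and on how complete those periods are. If treatment months are fixed 30-day blocks, as SAP 18.1.1 suggests, the adjustment would never operate after baseline.

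**Working it through.** The plan gives no figure on this point to reproduce.

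**Does another section override the trigger?** SAP 7.3 sends the reader to 18.2.2, which sends the reader back to 18.1.2. SAP 18.3.1 points to 18.1.1, which holds no missing-diary rule. SAP 6.2 does not say what happens to a 30-day baseline with gaps. Nothing overrides it.

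**Single participants** (formula in SAP 18.1.1)

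- Month incomplete. Baseline 8 (complete), then 4 migraine headache days in 24 of 30 entries. Raw: 1 - 4/8 = 50%, a responder. Rescaled: 4 × 30/24 = 5.0 and 1 - 5/8 = 37.5%, a non-responder.
- Baseline incomplete. 9 days in 27 of 30 entries, then 5 in a complete 30-day month. Raw: 1 - 5/9 = 44.4%, a non-responder. Rescaled: 9 × 30/27 = 10 and 1 - 5/10 = 50%, a responder.
- 75% threshold. Baseline 8 (complete), then 2 days in 24 of 30 entries. Raw: 75%. Rescaled: 2.5 days and 68.75%.
- 100% threshold. 0 × 30/x = 0, so nothing changes.

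**Effective threshold.** Let cb and ct be the completion of a baseline and a month left raw, and 1 for a rescaled period. In expectation a participant counts as a 50% responder when the true reduction is at least 1 - 0.5 × cb/ct.

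- Raw month at 90%, rescaled baseline: 1 - 0.5/0.9 = 44.4%.
- Raw baseline at 90%, rescaled month: 1 - 0.5 × 0.9 = 55.0%.
- Both raw, equal completion: 50.0%.
- Both raw, 87% then 97%: 1 - 0.5 × 0.87/0.97 = 55.2%.

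**Simulation (all inputs assumed).** 1.5 million draws per arm before eligibility. The latent baseline rate is gamma with mean 9 per 30 days and shape 6. Baselines are kept if the normalised count is 4 to 14 and completion is at least 80%. The remaining fraction is beta(2m, 2(1 - m)), with m = 0.44 and 0.545 in the two arms. Months are kept above 50% completion. Other months last 28, 29, 31 or 32 days, and other baselines 31 to 40 days. Completion is 90% unless stated. Cells show 50% response as literal / rescaled / complete diaries, in percent; shifts come from unrounded rates.

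| Scenario | Higher arm | Lower arm | Literal minus rescaled |
|---|---|---|---|
| Baseline rescaled, all months 30 days | 66.0 / 61.1 / 61.0 | 55.3 / 49.8 / 49.5 | +4.9 / +5.4 |
| Baseline rescaled, a fifth of months 30 days | 62.1 / 61.1 / 60.9 | 51.0 / 49.9 / 49.5 | +1.0 / +1.1 |
| 30-day baseline raw, a fifth of months 30 days | 58.6 / 61.5 / 61.3 | 47.3 / 50.3 / 50.0 | -2.9 / -3.0 |
| All periods raw, 90% throughout | 64.2 / 61.6 / 63.5 | 53.2 / 50.3 / 52.1 | +2.6 / +2.9 |
| All periods raw, baseline 87%, months 97% | 60.0 / 61.6 / 63.4 | 48.6 / 50.3 / 52.3 | -1.5 / -1.7 |

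With a fifth of months at 30 days and mixed baselines, the shift is -0.9/-1.0 if half of baselines last exactly 30 days, and +0.6/+0.7 if one in eleven does. For 75% response it is +3.4/+3.0 in the first row and -1.8/-1.6 in the third. Gamma shapes of 3 or 12 give +4.9 to +5.5 and -2.8 to -3.1 for those two rows.

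**Treatment difference, literal against rescaled.** First row 10.7 against 11.2; third row 11.3 against 11.2; largest shift found 10.3 against 10.9 (shape 3). With no true effect, a rescaled baseline, and completion of 90% in one arm and 85% in the other, the spurious difference is 2.8 points if all months are 30 days, 1.4 if half are and 0.6 if a fifth are.

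**How often is a month exactly 30 days?** If months follow visits within ±2 days: 20% with visit days uniform, 31% with weights 1:2:4:2:1, and 54% if two thirds of visits fall on the nominal day. With the extra day in SAP 17.1: 17%, 20% and 11%.

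**The case against.** The strongest reply is that the intent is plain. The heading, the equal-rate assumption, SAP 18.2.2 and the normalised counts in Appendix 3 all describe a missing-data correction, so a sensible programmer would rescale anyway. That is fair, and it makes this a wording defect rather than a deliberate analysis choice. But the SAP is the programming specification, and its operative sentence gives a different dataset from its rationale.

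Second, the primary summary measure is a difference between arms, and it hardly moves when completion is equal. This stands. The documents give no reason to expect unequal completion in a double-dummy trial.

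Third, the largest upward shift needs every treatment month to be exactly 30 days, and the downward shift needs a baseline left raw even though SAP 6.2 calls it normalised. Both are limits on size. SAP 6.2 can be read as covering length only, so it does not clearly rescue a 30-day baseline.

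Fourth, the rescaled rate is not always closer to the truth. With all periods raw at equal 90% completion, the literal rule is +0.7/+1.1 from complete diaries and the rescaled rule -1.9/-1.8. That also stands, but only because the two raw errors offset each other. In the other four tabulated scenarios rescaling is closer.

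**Conclusion.** The concern holds: the sentence as written gives a result that its own section contradicts, and it should be corrected. The misclassification of individual participants at 50% and 75% is plain arithmetic. The population effect rests on assumed completion, period lengths and response distributions. On those assumptions, absolute 50% response shifts by between about +5 and -3 points, and by about 1 point when baseline is rescaled and a fifth of months last exactly 30 days. The sign cannot be fixed from the documents. With equal completion the treatment difference moves by at most about 0.6 point, against the 12 points assumed in Protocol 9.5, so the superiority conclusion is not under serious threat unless completion differs by arm. 100% response is unaffected.

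**What to change.** In SAP 18.1.2, change the trigger to: *if the number of non-missing diary days x in the period is not equal to 30, multiply the count by 30/x*, and state that this applies to baseline and to every treatment month.

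Two small tidy-ups can go in at the same time. Point SAP 18.3.1 to 18.1.2 instead of 18.1.1. For the exploratory weekly counts, say that each week is scaled by 7/x, because Week 4 takes the 9 days left in a 30-day month (30 - 21 = 9).

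The cost is one clause, one cross-reference and one line, with no new data and no design change. It belongs in the final SAP, which Protocol 9 requires before unblinding.

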2.3. EXPLORATORY OBJECTIVES

The tertiary/exploratory objectives are listed in Table C and Table D.

Table C: Tertiary/Exploratory Objectives and Endpoints

Objectives	Endpoints
To compare galcanezumab with rimegepant with respect to change in participant global impression of the severity of migraine.	Mean change from baseline in the Patient Global Impression of Severity (PGI-S) at Month 3.
To compare galcanezumab with rimegepant with respect to change in moderate to severe headache days.	The overall mean change from baseline in the number of monthly moderate to severe headache days across the 3-month double-blind treatment period.
To compare galcanezumab with rimegepant with respect to change in Total Pain Burden.	Mean change from baseline in the Monthly Total Pain Burden across the 3-month double-blind treatment period.

Table D: Additional Exploratory Objectives and Endpoints.

Objectives	Endpoints
To assess onset of action*	
To compare galcanezumab with rimegepant with respect to weekly migraine headache days by Week 4, Week 3, Week 2, and Week 1	Mean change from baseline in the number of weekly migraine headache days in the months that galcanezumab was superior to rimegepant

Document: **CCI**

Author: **PPD**

Version Number:

3.0

Version Date:

19May2023

CCI

To compare galcanezumab with rimegepant with respect to rimegepant with respect to 50% response rate at Month 3, Month 2, and Month 1	Percentage of participants with $\geq 50\%$ reduction from baseline in monthly migraine headache days at Month 3, Month 2, and Month 1
To compare galcanezumab with rimegepant with respect to 50% response rate at weeks 4, Week 3, Week 2, and Week 1	Percentage of participants with $\geq 50\%$ reduction in Weekly migraine headache days at weeks 4, 3, 2, 1 in the months that galcanezumab was superior to rimegepant
To assess sustained response	
To compare galcanezumab with rimegepant with respect to onset of 50% sustained response	The initial month at which galcanezumab was superior to rimegepant in the proportion of patients meeting at least a 50% reduction in monthly migraine headache days that is sustained at all subsequent months through Month 3
To assess other endpoints of interest	
To compare galcanezumab with rimegepant with respect to change in use of acute headache treatment	The overall mean change from baseline in the number of monthly days with acute headache medication use during the 3-month double-blind treatment period

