6.4. WINDOWING CONVENTIONS

The following describes assignment of visit windows to the following data for purposes of analysis:

- Screening lasts from 3 to 30 days, approximately.
- Eligibility is determined between a minimum of 30 days and a maximum of 40 days.
- For scheduling purposes, a month is 30 days.

See Section 18.1.1. for the derivation of diary time periods. No other assignment of visit will be done – visit as collected will be used.

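### The diary-sufficiency rule works only by month, so for the exploratory weekly endpoints it can discard complete weeks and keep weeks with one or two diary days

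*SAP*

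**What the plan says.** SAP 18.1.2 rescales a period's migraine-day count by 30/x, where x is the number of non-missing diary days. It extends this approach to secondary and exploratory diary measures and gives no minimum x. If compliance for a monthly interval is 50% or less, "then all endpoints to be derived from the ePRO diary data for that one-month period will be considered missing". For a participant who stops early, the last month's compliance "will be calculated with the denominator of the maximum of 30 and the total number of calendar days in that month", so the denominator is never below 30.

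SAP 17 derives compliance only by month and overall: "Electronic patient reported outcomes diary compliance at each 1-month period (including baseline, Month 1, 2, 3", plus the whole treatment period. The denominator in 17.1 is "date of injection at the end of interval minus date of injection at the beginning of the interval +1", which is 31 for a 30-day interval.

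Weeks are cut inside months (SAP 18.1.2, secondary and exploratory measures): "For each month, the first 7 calendar days will be counted as week 1". Weeks 2 and 3 follow in the same way, and Week 4 takes the remaining days, 9 in a 30-day month. SAP 2.3, Table D, plans "To compare galcanezumab with rimegepant with respect to weekly migraine headache days by Week 4, Week 3, Week 2, and Week 1" and a weekly 50% response. A footnote defines weekly onset as the first week of superiority that is maintained through the rest of that month.

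The other diary rules are the migraine-attack rule (SAP 7.3.1), the 80% baseline eligibility criterion (Protocol 5.1) and the protocol-deviation rule (SAP Appendix 3). They also work on a month or a whole period.

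**The concern.** The rule's unit is the month, while the unit of these two endpoints is the week, and the mismatch acts in both directions. Fully recorded weeks are dropped when the rest of the month is empty. Nearly empty weeks are kept when the rest of the month is full.

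Reading the rule as covering monthly endpoints only would save the complete weeks, but the weekly endpoints would then have no sufficiency rule at all. Either reading leaves a gap for programmers to fill.

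At stake is the weekly onset description. A 50% response judged on one or two days depends largely on whether a migraine happened to fall on those days. The discarded complete weeks are observed data that the repeated-measures models could have used.

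**Working it through.** The plan gives no figure for the weekly endpoints, so there is none to reproduce.

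**1. The monthly rule applied to weeks.** Inputs: a 30-day month (SAP 6.4: "For scheduling purposes, a month is 30 days"), weeks of 7, 7, 7 and 9 days, and a month missing if compliance is 50% or less.

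- Leaves after Day 14, all diaries completed: 14/30 = 46.7%. Month missing; complete Weeks 1 and 2 lost.
- Leaves after Day 15: 15/30 = 50.0%. Same result.
- Leaves after Day 16: 16/30 = 53.3%. Month kept; Week 3 (Days 15 to 21) rests on 2 days.
- Stays in the study, 1 or 2 diaries in Week 1, all others completed: 24/30 = 80.0% or 25/30 = 83.3%. The sparse Week 1 is kept.

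With a denominator of 31 the cut is unchanged: 15/31 = 48.4% is missing and 16/31 = 51.6% is kept. Two complete weeks are not always lost, because the 9-day Week 4 plus any other full week makes 16 days.

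**2. Effect on weekly 50% response.** Assumptions not in the documents: independent days, no treatment effect, a weekly baseline of B × 7/30, and counts scaled by 7/x. B runs over the eligible range, 4 to 14 migraine days per 30. The daily probability is p = B/30. A week with k migraine days among x recorded days is a response if 7k/x ≤ 0.5 × B × 7/30, with k binomial(x, p).

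For B = 8 the threshold is 0.93, so response requires zero migraine days and has probability (1 − 8/30)^x.

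| B | 1 day | 2 days | 3 days | 4 days | 7 days |
|---|---|---|---|---|---|
| 4 | 0.867 | 0.751 | 0.651 | 0.564 | 0.367 |
| 8 | 0.733 | 0.538 | 0.394 | 0.289 | 0.114 |
| 9 | 0.700 | 0.490 | 0.343 | 0.240 | 0.329 |
| 14 | 0.533 | 0.284 | 0.152 | 0.081 | 0.087 |

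Over B = 4 to 14, a 1-day week scores response 53% to 87% of the time and a 2-day week 28% to 75%, against 9% to 37% for a full week. At each B, the 1-day and 2-day weeks exceed the full week. Weeks of 3 or 4 days fall on either side of it. With a true 50% reduction and B = 9, they give 0.614 and 0.522 against 0.717 for a full week.

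**3. Effect on the contrast between arms.** With true reductions of 60% and 40% and B = 8, the difference in response probability is 0.159 for a full week, 0.092 for 2 days and 0.053 for 1 day.

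**4. How often.** If m of 30 diaries are recorded at random, the probability that a 7-day week has 3 or fewer is hypergeometric: 0.42, 0.34 and 0.27 for m = 16, 17 and 18, but 0.016 for m = 24.

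For leavers, take the 10% dropout ceiling and 575 randomized (Protocol 9.5): about 58, with departures assumed to be spread evenly over the days of a month. Those leaving on Days 7 to 15 lose at least one complete week: 58 × 9/30 ≈ 17. Those leaving on Days 14 or 15 lose two: 58 × 2/30 ≈ 4. Those leaving on Days 16 or 17 leave a Week 3 of 2 or 3 days: also about 4.

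**The case against.** The strongest reply is that little depends on this. The endpoints are additional exploratory ones outside the testing hierarchy. Randomized participants had completed at least 80% of baseline entries, and at that level (24 of 30) sparse weeks are rare. Protocol 7.1 keeps participants in follow-up after they stop the intervention, and 7.2 expects discontinuation to be uncommon. The figure of 17 leavers uses the dropout ceiling and covers three months and both arms, so it is about 6 per month. All of that stands and limits the point to a minor one.

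A reader might infer that weekly response rates are pushed up generally. The calculation does not support that: 1-day and 2-day weeks are inflated, but 3-day and 4-day weeks can score below a full week. Nor does it extend to mean weekly change, where scaling by recorded days is unbiased under the SAP's own missing-at-random assumption and sparse weeks mainly add noise.

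A reader might also infer that the onset week moves, or that the lost weeks come mostly from people who stopped for poor efficacy or tolerability. The same rule applies to both arms of a blinded trial. The calculation shows a diluted contrast in sparse weeks, not a shift in onset, and the documents do not give the reasons for early departure.

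**Conclusion.** The point holds as a minor one. Followed as written, SAP 18.1.2 discards fully recorded weeks from participants who leave by Day 15 of a month, and keeps weeks of 1 or 2 days whenever the month exceeds 50%. No weekly minimum exists anywhere in the documents.

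The demonstrated distortion is in weekly 50% response, and its size rests on the independence, no-effect and 7/x-scaling assumptions stated above. Its frequency cannot be derived from the documents. It ranges from negligible at good compliance to substantial in months just above the cut, with at most about 17 leavers losing complete weeks under the even-spread assumption. Primary and key secondary endpoints are unaffected by this gap.

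**What to change.** In SAP 18.1.2, keep the monthly 50% rule for monthly endpoints. For the weekly endpoints, require that more than 50% of the week's own days are non-missing, whatever the month's compliance, and set the week to missing otherwise. That means at least 4 of 7 days, or at least 5 of 9 for Week 4 of a 30-day month. State also that retained weekly counts are scaled to a 7-day rate (7/x), because the text now gives only 30/x.

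The cost is a short SAP addition and one derivation step. Some sparse weeks become missing, and some distortion remains at the minimum: with B = 8 and no effect, a 4-day week still scores response 29% of the time against 11% for a full week.
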